#### 2.6 Unanticipated Adverse Events

Unanticipated adverse device effects refer to any event not identified above that represents a "serious adverse effect on health or safety or any life-threatening problem or death caused by, or associated with, a device if that effect, problem or death was not previously identified in nature, severity, or degree of incidence in the investigational plan or application, or any other unanticipated serious problem associated with a device that relates to the rights, safety, or welfare of subjects." [FDA 21 CFR 812.3(s)]

Investigators are to inform their respective Institutional Review Boards (IRBs) immediately if an unanticipated adverse device effect is suspected (no more than 10 working days after the investigator learns of the effect). If the case is determined to be an unanticipated adverse device effect, the investigator will fill out an "Unanticipated Adverse Device Effect Form." University of Iowa will report the results of an evaluation of the unanticipated adverse device effect to the FDA and all other reviewing IRBs and investigators within 10 working days after first receiving notice of the event.

#### 2.7 Data Analysis for Population 1

In order to assess the feasibility of using the L24 electrode arrays in adults, data will be analyzed individually and with group statistics. We will measure success of this study by assessing speech perception, localization, and music performance as described above in the test descriptions. We will attempt to compare these results with adults implanted with

standard-length devices on one or both ears on the same test measures. Efficacy of the Nucleus Hybrid L24 cochlear implant system will be determined by a comparison of preoperative (best aided) vs. postoperative outcomes measures. Efficacy will also be measured by statistically significant differences between mean, preoperative speech perception scores (best aided) and postoperative scores. The null hypothesis to be tested is that there is no difference for the subjects between their pre- vs. postoperative speech performance

Because this is a feasibility study, we will only be implanting up to 15 adults with the Nucleus Hybrid L24 cochlear implant. We recognize that this small number of subjects may not afford us enough statistical power to adequately answer all questions associated with the feasibility of using a short electrode device for the provision of acoustic and electric sound processing to adults who demonstrate severe sensorineural hearing loss. However, it may lend us foundational knowledge to assess whether the devices are beneficial to this population of adults.

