#### 2.5 Adverse Effects

Adverse effects are any undesirable clinical or medical occurrence associated with use of the device or participation in the study. Any adverse effects are to be reported to the FDA and our IRB via the "Adverse Effects Form". The Primary Investigator will be required to verify that there are or there are no adverse effects to report.

Adverse effects will be reported if observed, even if acknowledged as risk factors in the consent. Adverse effects include:

1. Sudden changes in residual low-frequency hearing. Specifically, a PTA at 125, 250, 500 HZ that is  $\geq 30$  dB HL.
2. Total loss of residual hearing
3. Vertigo, dizziness, or balance problems that did not exist preoperatively or worsened postoperatively
4. Facial nerve problems
5. Meningitis
6. Perilymphatic fistulae
7. Tinnitus that did not exist preoperatively or worsened postoperatively
8. Implant Migration/Extrusion
9. Skin flap problems
10. Device-related/programming problems
11. Infection requiring explantation
12. Device failure requiring explantation

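### Section 2.6 of the protocol stops any adverse effect listed in 2.5 from counting as unanticipated through severity or incidence, although the definition it quotes allows this

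*Protocol*

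**What the plan says.** Section 2.5 of the protocol lists 12 kinds of adverse effect. The reporting route is "Any adverse effects are to be reported to the FDA and our IRB via the" Adverse Effects Form, and section 2.5 adds: "Adverse effects will be reported if observed, even if acknowledged as risk factors in the consent". It states no time limit for that form.

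Section 2.6 sets a separate rule for unanticipated adverse device effects. Its lead-in is "Unanticipated adverse device effects refer to any event not identified above that represents a", followed by a quotation of the regulatory definition. That definition covers a serious effect, problem or death associated with the device "if that effect, problem or death was not previously identified in nature, severity, or degree of incidence in the investigational plan or application", and any other unanticipated serious problem.

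A suspected effect of this kind goes to the IRB promptly, "no more than 10 working days after the investigator learns of the effect". If it is confirmed, a dedicated form is completed. The university then reports its evaluation to the FDA and to all other reviewing IRBs and investigators "within 10 working days after first receiving notice of the event".

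**The concern.** The lead-in and the definition it introduces set different tests. The definition asks whether the nature, severity or incidence of the effect was foreseen. The lead-in asks first whether the event is on the list. A listed type that turns out more severe or more frequent than foreseen passes the definition and fails the lead-in.

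The list names foreseeable harms of the surgery and the device. For a foreseeable harm, the new information is usually that it is worse or more common than expected, and the severity and incidence parts of the definition exist to catch that. The study would implant up to 15 adults and up to 30 children and adolescents (15 with each array) and follow the younger group for five years. Someone deciding whether an event is a suspected unanticipated effect could stop at the lead-in, and the evaluation and wider notice in section 2.6 would then not start.

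**Working it through.** No arithmetic applies beyond counting, and the plan gives no figure to reproduce. The check sets the two sections side by side.

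**Step 1. The rule as written.** An event is unanticipated under section 2.6 only if (a) it is not identified above and (b) it meets the quoted definition. The sentence joins the two conditions, so both must hold.

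**Step 2. What 'above' contains.** Section 2.5 has 12 items:

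- Six carry some qualifier of degree or onset: item 1 (a 30 dB HL figure), item 2 (total loss), items 3 and 7 (new or worsened after surgery), and items 11 and 12 (explantation required).
- The other 12 − 6 = 6 are named by type only: facial nerve problems, meningitis, perilymphatic fistulae, implant migration or extrusion, skin flap problems, and "Device-related/programming problems".
- None of the 12 has an expected incidence.

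Item 10 is open-ended, so the reach of the exclusion also depends on how widely a site reads it.

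**Step 3. Apply both tests to the same serious, device-associated event.**

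| Event | Quoted definition alone | Section 2.6 as written |
|---|---|---|
| Type not listed in 2.5 and not previously identified | Qualifies | Qualifies |
| Listed type, severity and incidence as previously identified | Does not qualify | Does not qualify |
| Listed type, severity not previously identified | Qualifies | Does not qualify: fails (a) |
| Listed type, incidence not previously identified | Qualifies | Does not qualify: fails (a) |

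The tests disagree in the last two rows. Incidence gives the cleanest example. A cluster of meningitis cases with one array could be unexpected in frequency, yet meningitis is on the list, so condition (a) excludes it.

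**Step 4. What a listed event receives and what it loses.**

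| Element | Listed event (2.5) | Unanticipated effect (2.6) |
|---|---|---|
| Reported to the FDA and the IRB | Yes | Yes |
| Stated time limit for IRB notice | None | 10 working days |
| Determination whether unanticipated, with its own form | No | Yes |
| Evaluation report to the FDA, other reviewing IRBs and investigators | No | Yes, within 10 working days |

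**The case against.** **Listed events are reported anyway.** This stands. A reader might infer that listed events of unexpected severity or frequency escape reporting, and the documents do not support that. Section 2.5 sends every adverse effect to the FDA and the IRB, including those already named as risks in the consent. The loss is confined to the lower three rows of the table in Step 4. The timing of the Adverse Effects Form may also be set on the form or in IRB procedures that are not shown, so the claim is only that the protocol states none.

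**The list does address severity.** This stands in part. It would be wrong to say that every listed item lacks severity: total loss and the two explantation items carry one, and item 1 has a numeric threshold. But six items have no qualifier at all, and none of the 12 has an expected incidence.

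**The most extreme outcome may still qualify.** Death is not on the list and the definition names it separately, so a death following a listed event can be read as not identified above. This is a fair limit: one should not say that listed events are excluded however extreme the outcome. It does not help with severe or frequent non-fatal events.

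**Intent is clear because the regulation is quoted in full.** On this reading the lead-in is shorthand for what the plan has not previously identified, and a trigger based on suspicion leaves room for judgement. The reading is reasonable, but it adds words that the sentence does not contain. The quotation is subordinate to the lead-in, and the list gives no incidence against which the reading could be applied.

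**Expected severity and incidence may be in the application.** They may be. The application, the consent forms and the two referenced device submissions are not shown, so it cannot be said that expected rates were never stated. This does not remove the conflict, because the lead-in excludes what is identified above, not what is identified in the application.

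**Conclusion.** The point holds as a conflict within one safety-reporting sentence. Read literally, section 2.6 disables the severity and incidence parts of its own quoted definition for all 12 event types in section 2.5. The consequence is the absence of a stated deadline, of the unanticipated-effect determination and form, and of the timed evaluation report to the FDA, other reviewing IRBs and investigators. Reporting to the FDA and the IRB is not lost.

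The conclusion rests on reading the lead-in and the definition as joint conditions, which is how the sentence is built. It does not depend on any assumed event rate, and the documents give no basis for estimating how many events would be affected. No endpoint, analysis or sample size is touched. The correction is worth making because the rule governs safety reporting in a study that includes children and the change is small.

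**What to change.** Either delete the words 'not identified above' from the lead-in of section 2.6, so that the quoted definition alone decides, or reword the lead-in to follow it. Suggested wording: an unanticipated adverse device effect is any event meeting the definition below, including an event of a type listed in section 2.5 if its severity or incidence was not previously identified in the investigational plan or application.

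This is a one-sentence change. It alters no procedure, test schedule or analysis. The downside is possibly a few more expedited assessments.

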### **2.8 Data Analysis for Population 2**

In order to assess the feasibility of using the Nucleus Hybrid S12 and L24 electrode arrays in children and adolescents, data will be analyzed individually and with group statistics. We will measure success of this study by assessing speech perception, localization, speech/language development, and music performance as described above in the test descriptions. We will attempt to compare these results with age-matched children implanted with standard-length devices on one or both ears on the same speech perception and speech/language measures. Efficacy of the Nucleus Hybrid S12 and L24 cochlear implant systems will be determined by a comparison of preoperative (best aided) vs. postoperative outcomes measures. Efficacy will also be measured by statistically significant differences between mean, preoperative speech perception scores (best aided) and postoperative scores. The null hypothesis to be tested is that there is no difference for the subjects between their pre- vs. postoperative speech performance

Because this is a feasibility study, we will only be implanting up to 15 children (5-12 years of age) or adolescents (13-15 years of age) with the Nucleus Hybrid S12 and 15 children (5-12 years of age) or adolescents (13-15 years of age) with the Nucleus Hybrid L24 cochlear implants. We recognize that this small number of subjects may not afford us enough statistical power to adequately answer all questions associated with the feasibility of using a short electrode device for the provision of acoustic and electric sound processing to children who demonstrate severe sensorineural hearing loss. However, it may lend us foundational knowledge to assess whether the devices are beneficial to this population of children.

### **2.9 Longer Electrode Array Reimplantation**

Some individuals have elected to have the Nucleus Hybrid cochlear implant removed and replaced with a standard, long electrode-array cochlear implant. This has typically been in cases where individuals have experienced a complete loss of residual hearing. It is a case-by-case decision to replace the Hybrid L24 with a standard length implant. The implant only data provided in the unpublished data section demonstrates that the performance is similar to a standard length implant. If the subject is performing at the average performance level one would not necessarily benefit from a change in device.

Additionally, the insertion of an electrode array may alter the perception of speech and other sounds compared to their sound quality prior to implantation, this may be due to the use of an electrode array, and/or changes in residual hearing. Subjects who elect to be implanted with a standard cochlear implant in the test ear, in place of the Nucleus Hybrid L24 or S12 (whichever they are implanted with) cochlear implant, will be required to complete the study protocol as outlined above.

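### Could scores obtained with a replacement standard implant be counted as Hybrid results?

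*Protocol*

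**What the plan says.** Section 2.9 covers "Subjects who elect to be implanted with a standard cochlear implant in the test ear, in place of the Nucleus Hybrid L24 or S12" and states that they "will be required to complete the study protocol as outlined above". They therefore stay on the test schedules of sections 2.4.4 (adults, to 24 months) and 2.4.5 (children and adolescents, to 60 months). The same section says that replacement has typically followed loss of all residual hearing. In a paragraph that names the L24, it adds: "The implant only data provided in the unpublished data section demonstrates that the performance is similar to a standard length implant".

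Section 2.7 defines efficacy in adults by device: "Efficacy of the Nucleus Hybrid L24 cochlear implant system will be determined by a comparison of preoperative (best aided) vs. postoperative outcomes measures". It then states the hypothesis by subject: "The null hypothesis to be tested is that there is no difference for the subjects between their pre- vs. postoperative speech performance". Section 2.8 follows the same pattern for Population 2, beginning "Efficacy of the Nucleus Hybrid S12 and L24 cochlear implant systems will be determined by a comparison of" pre- and postoperative measures and closing with the same null hypothesis.

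Both sections also announce an external comparison with recipients of standard-length devices: "We will attempt to compare these results with adults implanted with" such devices in section 2.7, and "We will attempt to compare these results with age-matched children implanted with standard-length devices on one or both ears" in section 2.8.

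**The concern.** Sections 2.7 and 2.8 can be read in two ways. The efficacy sentence is about a Hybrid system, so a score obtained with a standard implant would not belong. The null hypothesis is about subjects before and after surgery, with no condition on the device worn, so such a score would belong. The listening modes in section 2.1 do not settle it, because they refer to a cochlear implant in general.

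If the second reading governed the group analysis, a mean labelled as the Hybrid result would mix two devices at every visit after a replacement. In the external comparison, some subjects on the Hybrid side would be wearing the comparator type of device. Replacement is also related to outcome: it typically follows the loss of the hearing that the Hybrid is meant to preserve. The subjects in whom the Hybrid did least well would then have their later scores supplied by another device.

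**Working it through.** The protocol states no figure on this point, so there is nothing to reproduce. The check has three parts.

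**1. What the text fixes.**
- Section 2.9 fixes continued testing after replacement.
- Sections 2.7 and 2.8 open with the feasibility of the named Hybrid arrays and tie efficacy to the named Hybrid systems. Section 2.2 lists the Hybrid implant as a component of each system.
- The null hypothesis closes the same paragraph and serves that aim. Its reference to subjects need not extend the test to a device that the paragraph treats as the comparator.
- No sentence says that post-replacement scores are pooled, and none says that they are excluded. The text is silent rather than contradictory.

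**2. Possible size.** Inputs from the protocol are up to 15 subjects per device group (sections 2.7, 2.8), adult test visits at 3, 6, 12 and 24 months (section 2.4.4), and paediatric visits at 4, 8, 12, 18, 24, 36, 48 and 60 months (section 2.4.5). The timing of replacement and the device difference D are assumptions.
- Weight of one subject: 1/15 = 6.7% of a group mean, or 1/30 = 3.3% if the two paediatric groups are pooled.
- Visits with a standard implant in place:

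| Assumed replacement | Adult visits | Paediatric visits |
|---|---|---|
| before the first visit | 4 of 4 | 8 of 8 |
| after 12 months | 1 of 4 | 5 of 8 |
| after 24 months | 0 of 4 | 3 of 8 |

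- Shift in a 15-subject mean with k replaced subjects: k × D / 15. For k = 1, D = 0 gives 0, and D = ±10 points gives ±10/15 = ±0.67 points. A strong assumption of k = 3 and D = 30 gives 3 × 30/15 = 6.0 points.

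**3. Which scores could be affected.** Section 2.1 defines hybrid stimulation as acoustic plus electric hearing in the same ear, and combined stimulation as bilateral acoustic hearing plus electric hearing. A subject with no residual hearing left in the implanted ear, the typical replacement case in section 2.9, cannot give a true hybrid or combined score under these definitions. Sections 2.4.4.1 and 2.4.5.1 say only that tests in each condition will be attempted. For speech perception, mixing would therefore fall mainly on electric-alone scores and, in adults, bimodal scores. For electric-alone listening, the section 2.9 statement quoted above points to a small D, at least for the L24. The 6.7% weight thus does not apply equally to every outcome at every later visit.

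**The case for a change.** The strongest case for a change is that the protocol itself creates the post-replacement data and itself words the efficacy comparison, so the gap is not purely one for an analysis plan. Replacement is foreseen and not random. The reassurance about similar performance concerns implant-only listening in a paragraph about the L24. It does not clearly cover the S12, which has 10 electrodes and an anticipated depth of 10 mm against 22 electrodes and 16 mm for the L24. It also speaks of average performance, whereas the subjects who seek replacement may be those below average. A few added sentences would cost little.

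Much of this stands as description. The narrow statement that such scores could be counted is true. The S12, replacements for other reasons, and the speech and language tests given in the bilateral condition remain open.

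It does not establish an error. Separate tabulation, analysis sets and sensitivity analyses after a device change are what an analysis plan normally settles. The obvious repair is not clearly better either. Restricting the main result to scores obtained with the Hybrid in place conditions on keeping the device, and so removes subjects who typically lost all their residual hearing. An analysis of all subjects regardless of device is equally defensible. Nothing in the protocol decides between the two.

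**Conclusion.** No change to the plan follows. Continued follow-up after replacement is sound, the efficacy wording points to the Hybrid systems, and no sentence requires standard-implant scores to be reported as Hybrid results. What is left open is a detail that analysts can be expected to fill sensibly. The design is single-subject, data are analysed individually as well as by group, and with at most 15 subjects per device group each replacement can be identified.

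The size is 0 to 0.7 points in a 15-subject mean per replaced subject, if the devices differ by 0 to 10 points in either direction. It grows in proportion for larger differences or more replacements, and somewhat if fewer than 15 are enrolled. The number and timing of replacements and the device difference are assumptions. The consequence is also limited because sections 2.7 and 2.8 present a feasibility study that may lack power, and describe the standard-length comparison only as something to be attempted.
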